## **6. Experimental Design**

This will be a single-arm, multiple-institution, two-stage phase II trial designed to evaluate the safety and effect of serial intradermal vaccinations of a DNA vaccine encoding PAP with or without rhGM-CSF, and co-administered with nivolumab, on serum PSA in patients with PSA-recurrent, non-metastatic, non-castrate prostate cancer. A total of 20-41 patients will be accrued, treated over a maximum of one year each, and followed for up to two years for evidence of radiographic progression. All subjects will be followed an additional 2 years after their last treatment for evidence of delayed adverse events. The treatment will be as follows:

Nivolumab 240 mg IV every two weeks x 6 beginning day 1, then every four weeks x 9 beginning week 12

pTVG-HP (100 µg) administered intradermally (i.d.) every two weeks x 6 beginning day 1, then every four weeks x 9 beginning week 12

rhGM-CSF (208 µg) administered intradermally (i.d.) every two weeks x 4 beginning week 4, then every four weeks x 9 beginning week 12 NOTE: Only administered to patients for whom serum PSA obtained week 4 > serum PSA obtained at day 1.

#### A. Study Arm Assignment and Toxicity Assessment

Patients with non-metastatic prostate cancer, with evidence of rising PSA, and a calculable PSA doubling time with at least 4 serum PSA values collected over a one-year period of time, will be invited to participate. Given the absence of significant adverse events observed in a previous phase I study, no adverse events > grade 2 are anticipated attributable to vaccine alone. Similarly, given the absence of grade 4 events observed among 26 patients with advanced castration-resistant metastatic prostate cancer treated with this vaccine in combination with pembrolizumab, we do not anticipate toxicity that has not been observed with nivolumab alone. While not common, previous immune-associated toxicities have been observed with nivolumab, including immune-mediated pneumonitis, colitis, hepatitis, hypophysitis, nephritis, hyperthyroidism, and hypothyroidism. Hence these may be anticipated events. All study patients will be evaluated for evidence of toxicity over time, and further accrual to the trial will halt and be reviewed by the UWCCC DSMC if the toxicity rate is deemed to be excessive. A toxicity rate of 30% for Grade 3 events or 10% Grade 4 events given an attribution of at least possibly related to study treatment will be considered excessive. Grade 3 limited site reactions (lasting < 48 hours) and fevers/chills (lasting < 48 hours) will be excluded from this assessment as expected possible adverse events of limited duration.

Continuous toxicity monitoring based on repeated significance testing with a Pocock boundary will be applied after the first 5 patients have been accrued and evaluated for toxicity. A toxicity rate  $p_0$  of at most 15% of Grade  $\geq 3$  toxicity events will be considered as acceptable while a toxicity rate  $p_1=35\%$  or more will be considered as unacceptably high. Assuming a boundary probability of 0.1 under  $p_0$ , the stopping boundaries of the repeated significance testing procedure within an arm are as follows: 2/5, 3/9, 4/12, 5/17, 6/21, 7/26, 8/31, 9/35, or 10/40. If the number of Grade  $\geq 3$  toxicities exceeds the boundaries, accrual will be temporarily suspended and the study will be reviewed for safety, dose modification and safety modification, and the study will be reviewed for safety by the UW DSMC (data and safety monitoring committee). Once the study is suspended, it would only be reopened if modifications could be made, and approved by the DSMC and the UW-IRB, to assure that patient safety is reestablished. If not, the study would be closed.

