due to nivolumab, but unlikely related (or unrelated) to pTVG-HP vaccine, no further nivolumab treatments will be given. However, Grade 3 or 4 events that would not limit continued treatment or intervention (e.g. lymphopenia or asymptomatic elevations of amylase or lipase) will not require holding the dosing or discontinuation of nivolumab. The specific management for nivolumab-associated adverse events (and the indications for delaying or discontinuing nivolumab treatment) are shown in the table below. In the absence of adverse events attributed to DNA vaccine, the patient will continue with DNA vaccine administration only as per protocol. However, if a patient develops a Grade 3 toxicity with an attribution of at least possibly related to pTVG-HP vaccine, both vaccine and nivolumab treatment will be held until the toxicity resolves to Grade 1 or less. If a patient develops a second Grade 3 event (or any Grade 4 event) believed at least possibly related to pTVG-HP vaccine, no further treatments (nivolumab or vaccine) will be given. The patient will remain on study, however, with collection of radiographic and laboratory data as per protocol. The rationale for these modifications is that patients could continue to benefit in terms of anti-tumor response and this could in fact be related to the development of other autoimmune toxicities, and patients who have toxicity from nivolumab could still potentially benefit from continued DNA vaccination. While rare overall, autoimmune events observed following nivolumab treatment of patients with melanoma typically resolved and did not necessarily lead to discontinuation of treatment.

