#### **C. UWCCC Data and Safety Monitoring Committee (DSMC) Study Progress Review and Oversight**

The review of Protocol Summary Reports (PSRs) enables the UWCCC DSMC to assess whether the study should continue, continue with modifications, be suspended, or be closed. Following their review, the UWCCC DSMC will notify the sponsor-investigator of their recommendation and the authority for continuing, modifying, suspending, or closing the protocol is the responsibility of the applicable sponsor-investigator, Principal Investigator, IRB, FDA or other regulatory authority associated with the protocol.

Based on the risk level of this study, as determined by the UWCCC Protocol Review and Monitoring Committee, PSRs must be submitted to the UWCCC DSMC by the UWCCC site on a quarterly basis.

The UWCCC site is responsible for ensuring participating sites enter data used to populate the PSRs in a timely manner into the UWCCC instance of OnCore. This data includes: accrual information, Serious Adverse Events (SAEs), response to treatment, events reportable to IRB (e.g., non-compliance, unanticipated problems).

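### Section 6.A sets two accrual-halting rules that disagree on the same data, and the stated 0.1 halt probability belongs to only one of them

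*Combined protocol and SAP*

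**What the plan says.** Both rules stand under the Study Arm Assignment and Toxicity Assessment heading of protocol section 6.A.

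**Percentage limits (first paragraph).** The action is that "further accrual to the trial will halt and be reviewed by the UWCCC DSMC if the toxicity rate is deemed to be excessive". What counts as excessive follows: "A toxicity rate of 30% for Grade 3 events or 10% Grade 4 events given an attribution of at least possibly related" to study treatment. Grade 3 site reactions and fevers or chills lasting under 48 hours "will be excluded from this assessment as expected possible adverse events of limited duration".

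**Pocock list (second paragraph).** Monitoring is continuous once 5 patients have been evaluated. A Grade 3 or higher rate of up to 15% is acceptable, and 35% or more is not. "Assuming a boundary probability of 0.1 under" the 15% rate, the boundaries "are as follows: 2/5, 3/9, 4/12, 5/17, 6/21, 7/26, 8/31, 9/35, or 10/40". The action applies when the number of Grade 3 or higher "toxicities exceeds the boundaries, accrual will be temporarily suspended" pending review.

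The second paragraph does not mention the 30% or 10% limits and has no Grade 4 component. It does not repeat the attribution rule or the exclusions. No sentence links the two paragraphs. Section 7 deals with Grade 3 and 4 events in the individual patient, and section 10 covers only the estimation of toxicity rates.

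**The concern.** Safety is a primary endpoint, and these paragraphs hold the only numerical rules for stopping accrual. A monitoring committee given both cannot tell from the text which applies when they point different ways, or when the percentage limits are to be checked. A bare percentage is sensitive to this. At small n one or two patients reach it, and repeated checking gives chance many opportunities to do so.

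The plan states one operating characteristic, the 0.1. If the percentage limits can also halt accrual, that figure describes part of the procedure only, and nothing describes the whole. The gap affects both the Grade 3 and the Grade 4 limit.

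**Working it through.** **Inputs.** From section 6.A: limits of 30% (Grade 3) and 10% (Grade 4); the nine listed boundaries; first look after 5 patients; acceptable rate 15%, unacceptable rate 35%; crossing probability 0.1. From sections 6 and 10.C: a maximum of 41 patients. Looks are taken up to n = 40, because a halt after the 41st patient cannot stop accrual. Patients are treated as independent.

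**Step 1: reproduce the plan's figure.** For a Pocock-type rule, look after every patient from the 5th. Halt at the smallest count r with P(X ≥ r | n, 0.15) ≤ a, using the same a at every look. The largest a that keeps the overall crossing probability at or below 0.10 is 0.0341.

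- At n = 5, P(X ≥ 2) = 0.165 is too large and P(X ≥ 3) = 0.0266 is small enough, so the rule halts at 3. That is one more than the listed 2/5, as the word exceeds requires.
- The same holds along the list: halt at 3/5, 4/9, 5/12, 6/17, 7/21, 8/26, 9/31, 10/35 and 11/40. Each listed n is the last at which its count applies.
- Overall crossing probability is 0.0988 at 15% and 0.919 at 35%. Had reaching the listed count been meant, it would be 0.290 at 15%.

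So the list is right under exceeds.

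**Step 2: set the two rules side by side.** The percentage limits are first met at ⌈0.30n⌉ Grade 3 patients or ⌈0.10n⌉ Grade 4 patients.

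| n | Pooled count that halts (list) | Grade 3 count meeting 30% | Grade 4 count meeting 10% |
|---|---|---|---|
| 5 | 3 | 2 | 1 |
| 9 | 4 | 3 | 1 |
| 12 | 5 | 4 | 2 |
| 17 | 6 | 6 | 2 |
| 21 | 7 | 7 | 3 |
| 26 | 8 | 8 | 3 |
| 31 | 9 | 10 | 4 |
| 35 | 10 | 11 | 4 |
| 40 | 11 | 12 | 4 |

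At n = 5, two Grade 3 patients (40%) or one Grade 4 patient (20%) meet a percentage limit while the list allows both. At n = 40, eleven Grade 3 patients (27.5%) exceed the list but are below 30%.

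**Step 3: halt probability if either rule can halt.** Classify each patient by worst grade, with probabilities p3, p4 and 1 − p3 − p4. Let S_n(a, c) be the probability of no halt so far with a Grade 3 and c Grade 4 patients:

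S_n(a, c) = (1 − p3 − p4)·S_{n−1}(a, c) + p3·S_{n−1}(a − 1, c) + p4·S_{n−1}(a, c − 1).

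The mass moves to halted if a + c exceeds the list or if, at a check of the percentage limits, a ≥ 0.30n or c ≥ 0.10n.

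A hand check at n = 5 with p3 = 12% and p4 = 3%: no halt needs no Grade 4 and at most one Grade 3 patient. That has probability 0.85⁵ + 5(0.12)(0.85⁴) = 0.4437 + 0.3132 = 0.757. The chance of halting at the first look is therefore 0.243, against 0.0266 under the list alone.

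Run through to n = 40 at a total rate of 15%, with every split inside both percentage limits:

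| Grade 3 + Grade 4 (assumed) | List only | Limits checked once, n = 21 | Limits checked at the listed n | Limits checked after every patient from the 5th |
|---|---|---|---|---|
| 15% + 0% | 9.9% | 9.9% | 24.6% | 30.7% |
| 12% + 3% | 9.9% | 11.3% | 39.5% | 45.2% |
| 10% + 5% | 9.9% | 15.4% | 51.3% | 56.7% |

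The first row isolates the Grade 3 limit. It adds nothing at a single look at n = 21, where both rules need 7, but it adds 14.7 to 20.8 percentage points when checked often.

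**Step 4: sensitivity at 12% + 3%, checking after every patient.** Starting at n = 10 instead of n = 5 gives 40.1%. Starting at n = 10 and requiring the rate to be strictly above the limit gives 21.8%. Starting at n = 21 with the original trigger gives 14.7%.

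**The case against.** **Two layers are legitimate.** A stricter Grade 4 limit beside a pooled limit is not in itself a contradiction. A halt under the first paragraph leads to committee review, not closure, and the wording leaves room for judgement. Review after an early related Grade 4 event is defensible, since the plan reports none among 26 patients given this vaccine with pembrolizumab. All of this stands, and it is why the probabilities above are not error rates. It does not say how the paragraphs relate.

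**Other oversight exists.** Section 12.A grades life-threatening or disabling events as Grade 4 and counts life-threatening or significantly disabling events as serious. Most clinical Grade 4 events would therefore reach the committee chair individually through the expedited reporting in sections 12.C and 12.D. Section 12.C adds that "PSRs must be submitted to the UWCCC DSMC by the UWCCC site on a quarterly basis", and section 14.B describes weekly group review. This reduces the consequence. None of it supplies a numerical boundary, and isolated Grade 4 laboratory values may not arrive by that route.

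**The definitions probably carry over.** The paragraphs are consecutive under one heading, so applying the first paragraph's attribution and exclusions to the list is natural. That is fair, but unstated. A reader might also infer a conflict with section 7, which lets nivolumab continue through some Grade 3 or 4 events such as asymptomatic amylase or lipase rises. The documents do not support that. Section 7 governs dosing of one patient, and section 6.A lists its own exclusions, which do not include those events.

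**The sizes rest on assumptions.** They do. For one toxicity profile the answer runs from 15.4% to 56.7% with the schedule alone. The plan does not fix the schedule, so it leaves that range open.

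**Conclusion.** The point holds. Section 6.A contains two halting rules that conflict on identical data in both directions, with nothing to reconcile them and no minimum n, look schedule or count boundary for either percentage limit. On the plain reading, that either rule can halt, 0.1 is not the halt probability of the procedure. At a 15% total rate it lies between 9.9% and 56.7% in the cases tabulated, and only a single or late check keeps it near 0.1. These figures assume independent patients, the stated grade splits and look schedules, and a halt when a limit is met.

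Three stronger inferences are not supported:

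- *The Pocock list is wrong.* It reproduces exactly.
- *The trial will halt wrongly about half the time.* The schedule, trigger and grade split are not given, and the committee keeps judgement.
- *The Grade 4 limit is never enforced.* That requires the list to operate alone, and nothing in the second paragraph withdraws the first. Nor is this only a Grade 4 problem, since the Grade 3 limit alone raises 9.9% to between 24.6% and 30.7% under frequent checking.

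This should be corrected. No view is taken on which clinical threshold is right.

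**What to change.** Reconcile the two paragraphs of section 6.A into one procedure:

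- State whether the Pocock list implements the percentage limits or adds to them.
- Use one attribution rule and one set of exclusions for every count, with patients as the unit.
- If a separate Grade 3 or Grade 4 limit is kept, at whatever rate the sponsor chooses, give it a minimum n and a repeated-testing boundary, and say whether meeting or exceeding it triggers the halt.
- State the halt probability of the whole procedure at the acceptable and unacceptable rates, with the assumed grade split.

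The cost is protocol wording and a short calculation, with no added patients or visits. The downside is that the overall halt probability may prove less favourable than 0.1.

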## **7. Definition and Management of Limiting Toxicities and Adverse Events**

A treatment-limiting toxicity will be defined as any Grade 3 or greater toxicity (using the NCI Common Terminology Criteria version 4), or a specific Grade 2 event as described below that affects agent dosing, with an attribution of at least possibly related to the study or treatment procedures, and occurring between the pre-study visit and within one month of the final study vaccine treatment or within 90 days of the last treatment with nivolumab (whichever is later). If a patient develops Grade 3 toxicity with an attribution of at least possibly related to nivolumab and unlikely related (or unrelated) to pTVG-HP, the nivolumab treatment will be held until the toxicity resolves to Grade 1 or less, with the vaccine schedule continuing as per protocol. In general, if a patient develops a second Grade 3 event (or any Grade 4 event) believed to be at least possibly

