### C. Study Design and Sample Size Calculation

The primary efficacy endpoint is the PSA complete response (PSA  $< 0.2$  ng/mL) rate. A confirmed PSA CR will be defined as one in which serum PSA at least 4 weeks later is  $< 0.2$  ng/mL, as per PCWG2 recommendations [67]. In this patient population, the PSA CR rate is expected to be less than 5% with standard care. Hence, the null hypothesis that the PSA complete response rate is at most 5% will be tested against the alternative hypothesis that the rate is greater than 5%. A PSA complete response rate of 20% or more, on the other hand, will be considered sufficient evidence to consider further clinical trial investigation. In order to ensure sufficient accuracy in the estimation of PSA complete response, an adequate number of patients should be enrolled in this study. However, in order to avoid treating patients with a potentially ineffective therapy, a Simon optimal two-stage design with one interim analysis for efficacy will be utilized.

In the first stage, 21 patients will be enrolled and evaluated for PSA response. If a PSA complete response is observed in at most one out of the 21 patients, then study will be terminated after the first stage. Otherwise, an additional 20 patients will be enrolled in the second stage for a total of 41 patients.

Assuming that the number of subjects with a PSA complete response is binomially distributed and using a Simon-optimal two-stage design, this design has a significance of 5% and 90% power for detecting a true success (PSA complete response) probability of 20%. If the true PSA complete response rate is only 5%, the study will be terminated after the first stage with 66% probability. The expected sample size is 27 under this scenario. If, however, the true efficacy response rate is 20%, the study will be terminated early with only 6% probability with an expected sample size of 40 patients. The two-stage procedure has 98% power to detect an efficacy response rate of 25% and 71% power to detect an efficacy response rate of only 15%. The operating characteristic of the proposed balanced two-stage design are summarized in the following table:

**Table 1** *Operating characteristics of the Simon-optimal two-stage design*

True PSA complete response rate	Probability of	Power	Expected
---------------------------------	----------------	-------	----------

	early stop after stage 1		sample size
5%	66%	6%	27
10%	36%	35%	34
15%	16%	71%	38
20%	6%	90%	40
25%	2%	98%	41

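### The toxicity halting rule in Section 6.A counts toxicities against per-patient boundaries; the stated 0.1 holds only if each patient counts once, and the text never says so

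*Combined protocol and SAP*

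**What the plan says.** Section 6.A (Study Arm Assignment and Toxicity Assessment) sets up continuous monitoring with a Pocock-type boundary. It "will be applied after the first 5 patients have been accrued and evaluated for toxicity". The acceptable rate p0 is given as "of at most 15% of Grade" 3 or higher toxicity events, and the unacceptable rate p1 is 35%. The limits are introduced by "Assuming a boundary probability of 0.1 under" p0 and "are as follows: 2/5, 3/9, 4/12, 5/17, 6/21, 7/26, 8/31, 9/35, or 10/40". The action clause says that if the number of Grade 3 or higher "toxicities exceeds the boundaries, accrual will be temporarily suspended", with safety committee review to follow. A suspended study reopens only if modifications can be made and are approved by the DSMC and the IRB; otherwise it closes.

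The preceding paragraph of 6.A also words its general toxicity thresholds in events. It excludes only short-lived site reactions and fevers or chills.

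Section 7 makes provision for more than one severe event in the same patient. For nivolumab, the text covers what happens "if a patient develops a second Grade 3 event (or any Grade 4 event) believed to be at least possibly" due to that drug. For the vaccine, there is a parallel clause: "If a patient develops a second Grade 3 event (or any Grade 4 event) believed at least possibly related to pTVG-HP vaccine". After a first Grade 3 event, the general text holds treatment until the toxicity resolves to Grade 1 or less.

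Section 10.C gives the maximum accrual, "for a total of 41 patients".

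**The concern.** The numerator and the denominator are in different units. A patient with two Grade 3 events adds two to the count and one to the sample size. Suppose that, among the first five patients, one has two Grade 3 events and another has one. Counting toxicities gives 3, which exceeds the limit of 2, and accrual is suspended. Counting patients gives 2, and accrual continues. The wording in 6.A leads to the first answer, while the stated 0.1 belongs to the second.

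Safety is a primary endpoint and this is its quantitative halting rule. A false crossing is costly, because reopening needs approved modifications. The limits are also set against rates that make sense as the proportion of patients affected (15% acceptable, 35% not), whereas a count of events does not estimate that proportion.

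**Working it through.** **Inputs.** From 6.A: p0 = 0.15, p1 = 0.35, limits b = 2, 3, 4, 5, 6, 7, 8, 9, 10 at n = 5, 9, 12, 17, 21, 26, 31, 35, 40, and suspension when the count exceeds b. From 10.C: at most 41 patients; no limit is listed after n = 40. The share q of affected patients who have a second Grade 3 or higher event is not in the documents, so it is an assumption and is varied.

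**Method.** Let f(j) be the probability that a patient contributes j to the count. The distribution of the running count s is updated patient by patient, P_n(s) = Σ_j f(j) · P_(n−1)(s − j). At each listed n, the probability on s > b is removed and added to the crossing probability.

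**Step 1: reproduce the stated 0.1.** Each patient counts once, so f(1) = 0.15 and f(0) = 0.85. First look: P(3 or more of 5) = 10 × 0.15³ × 0.85² + 5 × 0.15⁴ × 0.85 + 0.15⁵ = 0.0244 + 0.0022 + 0.0001 = 0.0266. Carrying the recursion on:

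| n | limit | cumulative crossing probability |
|---|---|---|
| 5 | 2 | 0.027 |
| 9 | 3 | 0.047 |
| 12 | 4 | 0.053 |
| 17 | 5 | 0.066 |
| 21 | 6 | 0.073 |
| 26 | 7 | 0.082 |
| 31 | 8 | 0.090 |
| 35 | 9 | 0.094 |
| 40 | 10 | 0.099 |

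The total is 0.0988, in line with 0.1 for a discrete rule. At 35% the same recursion gives 0.919. Applying each limit at every n up to its listed n, from patient 5 on, leaves 0.0988 unchanged. Suspending when the count reaches the limit, rather than exceeds it, gives 0.290. The stated figure is therefore reproduced by counting patients and requiring the limit to be exceeded.

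**Step 2: count events, with 15% of patients affected.** Now f(0) = 0.85, f(1) = 0.15(1 − q), f(2) = 0.15q. Both events are placed at the patient's own position in the sequence. For the first look with q = 0.2, f = (0.85, 0.12, 0.03), and P(total of 2 or fewer in 5 patients) = 0.85⁵ + 5 × 0.85⁴ × 0.12 + 5 × 0.85⁴ × 0.03 + 10 × 0.85³ × 0.12² = 0.4437 + 0.3132 + 0.0783 + 0.0884 = 0.9236. The crossing probability at n = 5 is thus 0.076 instead of 0.027.

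**Step 3: count events, with p0 read as 0.15 events per patient.** The proportion of patients affected is then 0.15/(1 + q), so that the mean count per patient is 0.15. For q = 0.2 this is 0.125.

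Crossing probability by the last listed boundary:

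| q (assumed) | p0 = 15% of patients | p0 = 0.15 events per patient |
|---|---|---|
| 0 | 0.099 | 0.099 |
| 5% | 0.143 | 0.122 |
| 10% | 0.188 | 0.141 |
| 20% | 0.274 | 0.170 |
| 30% | 0.356 | 0.191 |
| 50% | 0.501 | 0.220 |

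Both columns start at 0.099 and exceed 0.1 at every assumed share of 5% or more.

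**The case against.** The strongest reply is that toxicities is shorthand for patients with a toxicity. The denominators are patients, the first look is defined in patients, and Section 10 treats toxicity rates as binomial proportions, with standard errors in 10.C and Wilson score intervals in 10.D. The match to 0.1 in Step 1 points the same way. On that reading nothing is inflated and the defect is loose wording. This stands as evidence of intent, but it does not change the words that whoever tallies toxicities for the DSMC must apply, and the five-patient example shows that the two readings can give opposite decisions.

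A reader might infer that an acceptable regimen would in fact be suspended far more often than one time in ten. The documents do not support that as a flat statement:

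- They give no second-event share. At 5% the probability is only 0.12 or 0.14, depending on how p0 is read.
- Section 7 provides for a second Grade 3 event; it does not predict one. Its management table stops nivolumab at a first Grade 3 or 4 colitis, pneumonitis, neurologic event or (with a delay exception) hepatic event, although the vaccine may continue.
- The calculation treats second events as immediate. Treatment can last a year, so some would fall at later looks with higher limits or after accrual ends. The figures therefore lean towards the upper end for each assumed share.

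On the other side, Section 7 lets nivolumab continue through Grade 3 or 4 laboratory findings such as lymphopenia or asymptomatic amylase elevation, and the study calendar repeats blood counts and a chemistry panel that includes amylase at most visits. Repeat events in one patient are therefore plausible.

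A reader might also infer that a crossing closes the trial, or that it could never be interpreted. Neither follows. A crossing leads to committee review, and the committee can see how many patients contributed the events. The error is also in the cautious direction.

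**Conclusion.** The rule is wrong as written, in a limited way. It pairs an event count with per-patient boundaries, and its stated 0.1 is reproduced (0.099) only under per-patient counting. If events are counted, the false-suspension probability is higher whenever repeat events can occur. With assumed second-event shares of 5% to 50%, it is about 0.14 to 0.50 if p0 means 15% of patients, and about 0.12 to 0.22 if p0 means 0.15 events per patient. Those ranges rest on an assumed share, at most two events per affected patient, and immediate counting of the second. The mismatch itself needs none of these assumptions. The correction should be made because the text permits two different suspension decisions from the same data.

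**What to change.** In 6.A, define the numerator as the number of patients with at least one qualifying Grade 3 or higher toxicity, each patient counted once, and describe p0 and p1 as proportions of patients. Keep the boundaries and the must-exceed trigger as they are; together they then deliver the stated 0.1. Report repeat events descriptively to the DSMC.

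The cost is about one sentence, with no change to the boundaries or the sample size. The small downside is that repeat events in one patient no longer move the boundary; they are still recorded as adverse events and handled individually under Section 7.
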